
Section 9.7.8 Month 1 Procedures Section 9.7.10
	
9.7.10 Post-Titration visit Procedures
 
Insertion
 
 In the event it is not feasible for the subject to return to the site for the above referenced 	
9.7.10 1-Month Post-Titration visit Procedures
 
 Perform a physical examination. In the event it is not feasible for the subject to return to the site for the above referenced 	
Physical Exams have been added one month after each dose adjustment for added safety monitoring. Options for safety monitoring assessments are provided

Section	Original Text (Amendment 3, 07 September 2016)	Revised Text (Version 4, 10 May 2017)	Justification for Change
1-Month Post-Titration visit Procedures	
procedures, the following alternative visit procedures are available to help ensure compliance with the Month 1 visit requirements:
 
Insertion (9.7.8)
 
Insertion (9.7.10)
	
procedures, the following alternative visit procedures are available to help ensure compliance with the Month 1 visit laboratory requirements:
 
 - A physical examination should be performed at the Month 3 visit if an onsite Month 1 visit was not performed. - A physical examination should be performed at the next scheduled visit if an onsite post-titration visit was not performed. 	
when returning to the site presents significant burden on the subject.

Section 9.7.11 Month 6 Procedures
 
Section 9.7.16 Month 6 Continued Follow-Up Procedures
	
Insertion
 
Insertion in 9.7.11 (not 9.7.16)
	
 • Perform TE at all study sites with access to Fibroscan® TE device. • Perform an ultrasound for HCC surveillance (if equipment is unavailable, sites should make every attempt to use available community referral sites). • Perform a physical examination 	
Fibroscan® TE monitoring has been increased to every 6 months to facilitate monitoring for progression to cirrhosis.
 
Hepatic ultrasound has been increased to every 6 months to conform to AASLD and EASL guidelines for PBC patients with cirrhosis.

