5.6. Importance of Monitoring of Disease Progression

Given PBC is a chronic, progressive liver disease, it is important that subjects with PBC are closely monitored to ensure early identification of potential disease progression to cirrhosis, decompensation and/or liver injury. More extensive safety monitoring and appropriate dosing adjustments, interruptions, and discontinuations will be implemented to improve subject oversight and safety. Investigators, together with the Sponsor's Medical Monitor, will consistently and frequently assess individual subjects to determine on an ongoing basis the totality of a subject's clinical profile, which includes careful evaluation of signs and symptoms of potential hepatic injury and/or decompensation coupled with rules based laboratory monitoring.

Subjects will be monitored for potential hepatic injury and/or decompensation and progression to cirrhosis ([Section 7.5](#)). Criteria for implementing dosing adjustments, interruptions, or discontinuations, and close monitoring procedures postdose-adjustment are described in [Section 7.6](#) and [Section 7.7](#). The more extensive monitoring is important given the elevated risk of decompensation and potential for higher hepatic exposure to OCA in this population.

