Visit Windows (+/-) ^c	±2 wk	±1 wk	±2 wk	±2 wk	±2 wk	±2 wk
Markers of Hepatic Fibrosis and/or Inflammation ⁿ			X		X	X
Genetics ^o					X	

AE = adverse event; β -hCG = beta human chorionic gonadotropin; EOS= End of Study; EOT = End of Treatment; FGF-19 = fibroblast growth factor-19; FIS = Fatigue Impact Scale; IP = Investigational Product; M = month, MRS = Mayo Risk Score; TE = transient elastography; VAS = Visual Analogue Scale; wk = week

^a Post-Titration Visits must be performed 1 month (± 1 week) and 2 months (± 1 week) after any up-titration in dose and/or frequency in subjects following modified dosing due to Child-Pugh B and Child-Pugh C hepatic impairment. See [Appendix A](#) for additional guidance. In subjects following the standard dosing regimen, the Post-Titration visit must only be performed 1 month (± 1 week) and 2 months (± 1 week) after the first up-titration to 10 mg OCA or matching placebo.

^b As soon as possible upon study discontinuation and as near as possible to last dose taken.

^c Visits should be based on Day 0 (not on the prior visit) with the exception of the Post-Titration Visit, which is based on the date of titration.

^d The yearly physical exam will include an assessment of smoking and alcohol consumption history and current habits for both.

^e Child-Pugh Score will be calculated based on ascites assessment, hepatic encephalopathy grade, and central laboratory evaluations per the Child-Pugh scoring system noted in the case report form.

^f The EQ-5D-5L and FIS Quality of Life questionnaires are validated for use in multiple languages. If a validated translation is not available in the local language required for a specific study subject, the data from that questionnaire will not be collected (See [Section 11.1.2.2](#) and [Section 12.2.5](#)).

^g Transient elastography (TE) will be conducted at 6-month intervals at all study sites where the Fibroscan® TE device is available.

^h Endoscopy will be conducted at all study sites where the device is available to assess for the presence of oesophageal varix/varices.

ⁱ Ultrasound will be conducted to enhance HCC surveillance. For all on study (eg, postday 0) ultrasounds: unless HCC has already been confirmed by biopsy, a second confirmatory image (eg, MRI) should be obtained to confirm suspected HCC.

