9.7.5. Months 1, 2 Procedures

- Perform a physical examination.
- Assess and record AEs
- Review and record prior and concomitant medications.
- Assess investigational product compliance, perform investigational product accountability, and review dosing diary with the subject.
- Obtain blood samples for serum chemistry, hematology, and coagulation tests.
- Perform assessments for calculation of Child-Pugh Score.
- Review progression to cirrhosis algorithm.
- Provide the subject with a dosing diary to document his or her dosing.
- In the event it is not feasible for the subject to return to the site for the above referenced procedures, the following alternative visit procedures are available to help ensure compliance with the Month 1 and Month 2 visit laboratory requirements:
 - At the Day 0 visit, the subject can be provided with the central laboratory collection kit and shipping materials associated with the Month 1 visit, and have the laboratory specimen collection performed at his or her local doctor's office or designated laboratory collection center. The subject must also be contacted via telephone at the visit timepoint to assess AEs, review concomitant medications, and assess investigational product compliance;
 - If all other options for the collection of the Month 1 and Month 2 laboratory samples have been exhausted, the use of a local laboratory for the Month 1 samples would be accepted for this visit; although, any laboratory data obtained from a local laboratory will not be captured in the eCRF or included in the study analysis. A copy of the local laboratory report would need to be provided to the Investigator for review and available in the source records. The Investigator should contact the Medical Monitor as soon as possible to discuss any local laboratory values that may be of clinical concern. The subject must also be contacted via telephone at the visit timepoint to assess AEs, review concomitant medications, and assess investigational product compliance;

- A physical examination should be performed at the Month 3 visit if an onsite Month 1 or Month 2 visit was not performed.
- Schedule the next visit, reiterate dosing instructions, and advise the subject:
 - NOT to take investigational product on the morning of the next visit, and
 - To bring the investigational product bottle(s); s/he will dose at the clinic (if this is in compliance with the established dosing frequency), and

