9.7.7. Post-Titration Visit Procedures

- Perform a physical examination.
- Assess and record AEs.
- Review and record prior and concomitant medications
- Assess investigational product compliance, perform investigational product accountability, and review dosing diary with the subject.
- Obtain blood samples for serum chemistry, hematology, and coagulation tests.
- Perform assessments for calculation of Child-Pugh Score.
- Review progression to cirrhosis algorithm
- Provide the subject with a dosing diary to document his or her dosing.
- In the event it is not feasible for the subject to return the site for the above referenced procedures, the following alternative visit procedures are available, to help ensure compliance with the Post-Titration laboratory requirements:
 - At the Up-titration Visit, the subject can be provided with the central laboratory collection kit and shipping materials associated with the Post-Titration Visit, and have the laboratory specimen collection performed at his or her local doctor's office or designated laboratory collection center. The subject must also be contacted via telephone at the Post-Titration Visit timepoint to assess AEs, review concomitant medications, and assess investigational product compliance;
 - If all other options for the collection of the Post-Titration laboratory samples have been exhausted, the use of a local laboratory for the Post-Titration samples would be accepted for this visit; although, any laboratory data obtained from a local laboratory will not be captured in the eCRF or included in the study analysis. A copy of the local laboratory report would need to be provided to the Investigator for review and available in the source records. The Investigator should contact the Medical Monitor as soon as possible to discuss any local laboratory values that may be of clinical concern. The subject must also be contacted via telephone at the Post-Titration Visit timepoint to assess AEs, review concomitant medications, and assess investigational product compliance;
 - A physical examination should be performed at the next scheduled visit if an onsite Post-Titration Visit was not performed
- Schedule the next visit, reiterate dosing instructions, and advise the subject:
 - NOT to take investigational product on the morning of the next visit, and

- To bring the investigational product bottle(s); s/he will dose at the clinic (if this is in compliance with the established dosing frequency), and

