- Subjects who develop cirrhosis during the course of the trial with a classification of Child-Pugh B or C
- Subjects with pre-existing cirrhosis who demonstrate a change in the Child-Pugh Score from A to B or C at any point in the study

Subjects may titrate dose and dosing frequency up or down as appropriate, within the dosing regimen. Up-titration should be done per Investigator discretion and be guided by the pre-titration tolerability assessments outlined in [Section 7.4.1](#). A 1-Month and 2-Month Post-Titration Assessment must be performed any time a subject's dose or frequency is up-titrated (see [Section 7.1.2](#) and [Section 9.7.7](#)).

Unscheduled Titration Visit, Optional Visit

An unscheduled up-titration visit may be scheduled for as early as 6 weeks after the initial titration visit (or subsequent titration visit) occurs for subjects who are following the modified dosing regimen. The visit procedures required for the unscheduled titration visit are outlined below. Subjects who up titrate at an unscheduled visit will continue to follow the regular visit schedule for all other study visits.

For subjects who up titrate at an unscheduled visit the following procedures will be performed:

- Assess and record AEs.
- Review and record concomitant medications.
- Perform the pre-Titration Tolerability Assessment as outlined in [Section 7.4.1](#).
- Assess the subject's supply of investigational product to ensure an adequate amount. Access the IWRS and dispense investigational product if necessary.
- Provide the subject with a dosing diary to document his or her dosing.
- Schedule the next visit, reiterate dosing instructions, and advise the subject:
 - NOT to take investigational product on the morning of the next visit, and
 - To bring the investigational product bottle(s); s/he will dose at the clinic (if this is in compliance with the established dosing frequency), and
 - To fast overnight (at least 8 hours) prior to the next visit. Fasting is required prior to all study visits, but water is permitted.

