For subjects who up-titrate at an unscheduled visit: The ± 1 -week window related to the 2-month Post-Titration Visit can be modified to occur 2 weeks earlier or 2 weeks outside of the allowed visit window to allow for the post-titration assessment to be performed during one of the subject's regularly scheduled study visits. If the 2-month Post-Titration Visit is performed during a regularly scheduled study visit, all scheduled procedures associated with that visit should be performed.

**APPENDIX B. ETHICAL CONDUCT ACCORDING TO THE
DECLARATION OF HELSINKI FOR COUNTRIES
PARTICIPATING OUTSIDE THE US (DECLARATION
OF HELSINKI, FORTELEZA, BRAZIL, 2013)**

Special Communication

World Medical Association Declaration of Helsinki Ethical Principles for Medical Research Involving Human Subjects

World Medical Association

Adopted by the 18th WMA General Assembly, Helsinki, Finland, June 1964, and amended by the:
 29th WMA General Assembly, Tokyo, Japan, October 1975
 35th WMA General Assembly, Venice, Italy, October 1983
 41st WMA General Assembly, Hong Kong, September 1989
 48th WMA General Assembly, Somerset West, Republic of South Africa, October 1996
 52nd WMA General Assembly, Edinburgh, Scotland, October 2000
 53rd WMA General Assembly, Washington, DC, USA, October 2002 (Note of Clarification added)
 55th WMA General Assembly, Tokyo, Japan, October 2004 (Note of Clarification added)
 59th WMA General Assembly, Seoul, Republic of Korea, October 2008
 64th WMA General Assembly, Fortaleza, Brazil, October 2013

Preamble

1. The World Medical Association (WMA) has developed the Declaration of Helsinki as a statement of ethical principles for medical research involving human subjects, including research on identifiable human material and data.

The Declaration is intended to be read as a whole and each of its constituent paragraphs should be applied with consideration of all other relevant paragraphs.

2. Consistent with the mandate of the WMA, the Declaration is addressed primarily to physicians. The WMA encourages others who are involved in medical research involving human subjects to adopt these principles.

General Principles

3. The Declaration of Geneva of the WMA binds the physician with the words, "The health of my patient will be my first consideration," and the International Code of Medical Ethics declares that, "A physician shall act in the patient's best interest when providing medical care."

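### After an off-site 1-month Post-Titration Visit, a Child-Pugh B/C subject can double from 10 to 20 mg per week from day 42, before the deferred physical examination falls due (day 52 at the earliest)

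*Protocol*

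**What the plan says.** Protocol 7.1.2 (footnotes to Tables 1 and 2) and Appendix A make Post-Titration Visits at 1 and 2 months mandatory after any up-titration on the modified regimen. Section 9.7.7 lists a physical examination among their procedures. It also allows an off-site alternative (a blood sample taken elsewhere plus a telephone contact) and then states: "A physical examination should be performed at the next scheduled visit if an onsite Post-Titration Visit was not performed".

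Section 7.3 and Appendix A (Table 13) set the steps: 5 mg once weekly, then 5 mg twice weekly (Titration 1), then 10 mg twice weekly (Titration 2). On the timing of the second step Appendix A says: "An unscheduled up-titration visit may be scheduled for as early as 6 weeks after the initial titration visit". It adds: "The visit procedures required for the unscheduled titration visit are outlined below". The list covers adverse events, concomitant medications, the 7.4.1 tolerability assessment, drug supply, the diary and scheduling. Section 7.4.1 asks for a review of adverse events and of safety laboratory results no more than 2 months old. Neither contains a physical examination.

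The first step is handled differently. Section 9.7.5 says: "A physical examination should be performed at the Month 3 visit if an onsite Month 1 or Month 2 visit was not performed". Month 3 is also the first visit at which Titration 1 is allowed.

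**The concern.** The two rules were written separately, and together they can put a safety check after the decision that it should precede. The examination belongs to follow-up of the step to 10 mg per week. On this path it may first take place when the subject is already on 20 mg per week.

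The summary of changes to Version 4 gives the reason for these examinations: "Physical Exams have been added one month after each dose adjustment for added safety monitoring". That log is cited only for purpose; the rule itself stands in the current 9.7.7. Section 5.6, which concerns subjects with PBC in general, says: "The more extensive monitoring is important given the elevated risk of decompensation and potential for higher hepatic exposure to OCA in this population". Subjects on the modified regimen have moderate or severe hepatic impairment, so the sentence applies to them with particular force. At stake is the order of one bedside check in a fragile subgroup. The efficacy analysis is not involved.

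**Working it through.** **Inputs**
- Earliest Titration 2: 6 weeks after Titration 1 (7.3, 7.4, Appendix A).
- Post-Titration Visits: 1 month and 2 months after the titration date, each ±7 days (9.7.1).
- Regular visits: quarterly, ±14 days, counted from Day 0 (9.7.1).
- Doses: 5 mg twice weekly after Titration 1; 10 mg twice weekly after Titration 2.
- Assumption: Titration 1 is given at a regular quarterly visit. Month lengths are taken over all calendar start dates in a 4-year cycle.

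**The plan's own figure.** 6 × 7 = day 42 after Titration 1. Weekly dose: 2 × 5 = 10 mg before and 2 × 10 = 20 mg after, a doubling.

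**1-month visit.** One calendar month is 28 to 31 days. 28 − 7 = 21 and 31 + 7 = 38, so the visit falls on days 21 to 38, always before day 42.

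**Where the deferred examination lands.** The next scheduled visit after the 1-month visit is the 2-month visit. Two calendar months are 59 to 62 days.
- Window opens: 59 − 7 = 52 to 62 − 7 = 55.
- Window closes: 59 + 7 = 66 to 62 + 7 = 69.

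If the 2-month visit is also off site, the examination moves on to the next quarterly visit. Quarterly gaps are 89 to 92 days. With Titration 1 taken 14 days late and the next visit 14 days early, the shortest gap is 89 − 28 = 61 days. No regular visit can therefore bring the examination forward to before day 52.

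**Size of the gap with Titration 2 on day 42 and an on-site 2-month visit**
- Shortest: 52 − 42 = 10 days, and 10 × 2/7 = 2.9 doses.
- Longest: 69 − 42 = 27 days, and 27 × 2/7 = 7.7 doses.

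The deferred examination thus follows the doubling by 10 to 27 days, after about 3 to 8 doses of 10 mg.

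**Does the flexible window close the gap?** Appendix A lets the 2-month visit shift: it "can be modified to occur 2 weeks earlier or 2 weeks outside of the allowed visit window". Arithmetically 52 − 14 = 38, which is before day 42. But the provision applies only to subjects who up-titrated at an unscheduled visit, and only to merge the 2-month visit with a regular one. Titration 1 was given at a regular visit, and no regular visit falls before day 61. The shift therefore serves follow-up after Titration 2 and does not move the examination at issue.

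**The case against.** The strongest reply is that nothing contradicts: a site can follow both 9.7.7 and Appendix A as written. A physical examination is also not a general condition for up-titration. Eligibility is set by 7.4.1, and several regular visits at which titration is assessed have no routine examination either: Month 3 unless catching up, Month 9, and the Month 3, 6 and 9 follow-up visits from Year 2. This stands. The point is only about the order of an examination that the protocol itself ties to the previous step.

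Safeguards also remain. Adverse events and laboratory results are reviewed before the step, interruption and discontinuation rules apply throughout, and the unscheduled titration is optional and at the Investigator's discretion. Section 9.7.16 lets the Investigator do more at an unscheduled visit. That also stands and limits the severity, but 9.7.16 permits an examination without requiring one. Nor can the titration visit readily count as the next scheduled visit, since the protocol calls it unscheduled and gives it its own list.

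Two stronger readings are tempting and are not supported.
- A reader might infer that, when the 1-month sample is read by a local laboratory, no Child-Pugh score on the current dose can exist before Titration 2. Section 12.2.6 calls for the score at all visits, and 9.7.16 allows additional laboratory tests at an unscheduled visit, so a score can be obtained.
- From Year 2 the routine examination is annual (7.1.2, Table 2: "The yearly physical exam will include an assessment of smoking and alcohol consumption history"). A reader might infer that this gap leaves subjects unexamined for most of a year. A long interval of that kind mainly reflects the annual schedule. Ascites and encephalopathy, the signs that enter the Child-Pugh score (7.5.5), are assessed at every quarterly visit, including the one at which Titration 1 is given.

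**Conclusion.** The gap is real and minor. For a Child-Pugh B/C subject whose 1-month visit after Titration 1 was off site, the protocol permits the step from 10 to 20 mg per week from day 42, while the examination deferred from that visit is due no earlier than day 52. The first titration step has a catch-up rule that avoids this; the second has none.

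The conclusion rests on Titration 1 being given at a regular visit and on the unscheduled titration visit not counting as a scheduled one. It needs four things together: the modified regimen, an off-site 1-month visit, use of the optional unscheduled visit, and Titration 2 before the deferred examination. The protocol gives no basis for estimating how many subjects this would be. One check is displaced and the others remain. Sample size, power, type I error and the endpoint are not affected.

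**What to change.** Keep the 6-week interval and 7.4.1 as they are. Add one line to the Appendix A list for the unscheduled titration visit: *If the preceding 1-month Post-Titration Visit was not performed on site, perform the deferred physical examination at this visit before up-titrating.*

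This mirrors the Month 3 catch-up in 9.7.5. It is a cheap improvement: one line of protocol text, with no new visit or blood draw. Because the 2-month visit keeps its own examination under 9.7.7, the downside is at most one additional routine examination per affected subject, at a visit that the subject already attends.

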APPENDIX C. REFERENCE LABORATORY VALUES FROM CENTRAL LABORATORIES

Covance Central Laboratories (Indianapolis, Indiana, US [for North America and Latin America regions]; Geneva, Switzerland [for Europe]; and Singapore [for Asia-Pacific region]) will serve as the central labs for analysis or specimen management for the analytes listed in the Table 12 of Protocol 747-302 Version 4. The following in text table provides the Covance Laboratory reference ranges for the pertinent liver biochemistries analyzed by Covance. These reference ranges are sex and/or age specific, and can change during the course of the clinical trial; therefore, investigative sites should always refer to the reference ranges available on the Covance issued laboratory reports.

		Covance Indianapolis		Covance Geneva and Covance Singapore	
Analyte	Sex	Age ^a	Reference Range	Age ^a	Reference Range
Albumin	Both	18Y – 69Y	SI Units: 33-49 g/L Conventional Units: 3.3-4.9 g/dL	18Y – 69Y	33-49 g/L
		69Y-80Y	SI Units: 33-46 g/L Conventional Units: 3.3-4.6 g/dL	69Y-80Y	33-46 g/L
		80Y-150Y	SI Units: 30-46 g/L Conventional Units: 3.0-4.6 g/dL	80Y-150Y	30-46 g/L
ALP	Female	18Y - 50Y	31-106 U/L	18Y - 50Y	31-106 U/L
		50Y - 60Y	35-123 U/L	50Y - 60Y	35-123 U/L
		60Y - 70Y	35-123 U/L	60Y - 70Y	35-123 U/L
		70Y - 80Y	35-123 U/L	70Y - 80Y	35-123 U/L
		80Y - 90Y	35-135 U/L	80Y - 90Y	35-135 U/L
		90Y – 150Y	35-140 U/L	90Y – 150Y	35-140 U/L
ALP	Male	18Y - 50Y	31-129 U/L	18Y - 50Y	31-129 U/L
		50Y - 60Y	35-131 U/L	50Y - 60Y	35-131 U/L
		60Y - 70Y	35-125 U/L	60Y - 70Y	35-125 U/L

		Covance Indianapolis		Covance Geneva and Covance Singapore	
Analyte	Sex	Age ^a	Reference Range	Age ^a	Reference Range
		70Y - 80Y	35-130 U/L	70Y - 80Y	35-130 U/L
		80Y - 90Y	35-125 U/L	80Y - 90Y	35-125 U/L
		90Y - 150Y	35-125 U/L	90Y - 150Y	35-125 U/L
ALT	Female	18Y - 69Y	6-34 U/L	18Y - 69Y	6-34 U/L
		69Y - 150Y	6-32 U/L	69Y - 150Y	6-32 U/L
ALT	Male	18Y - 69Y	6-43 U/L	18Y - 69Y	6-43 U/L
		69Y - 150Y	6-35 U/L	69Y - 150Y	6-35 U/L
AST	Female	18Y - 59Y	9-34 U/L	18Y - 59Y	9-34 U/L
		59Y - 150Y	9-34 U/L	59Y - 150Y	9-34 U/L
AST	Male	18Y - 59Y	11-36 U/L	18Y - 59Y	11-36 U/L
		59Y - 150Y	11-36 U/L	59Y - 150Y	11-36 U/L
Direct Bilirubin	Both	18Y - 150Y	SI Units: 2-7 umol/L Conventional Units: 0.1-0.4 mg/dL	18Y - 150Y	2-7 umol/L
Indirect Bilirubin	Both	0Y - 150Y	SI Units: 0-21 umol/L Conventional Units: 0.0-1.2 mg/dL	0Y - 150Y	0-21 umol/L
Total Bilirubin	Both	18Y - 150Y	SI Units: 3-21 umol/L Conventional Units: 0.2-1.2 mg/dL	18Y - 150Y	3-21 umol/L

ALP = alkaline phosphatase; ALT = alanine aminotransferase; AST = aspartate aminotransferase; Y = years; SI=International System of Units

^a The unstated word “to” is implied by the “dash” appearing in age specific reference ranges. A range such as “0-59 years” and “59-150 years” means: “0 up to but not including 59 years” and “59 up to but not including 150 years”.

Source: Covance Laboratory Services Manual Version 5.0.0. Dates vary by region: 10 Nov 2016 (North America), 22 Nov 2016 (Europe and Singapore)

